7.5. Method of Treatment Assignment

Participants will be randomized in a 1:1 ratio to placebo (ascorbic acid), or LPV/r, at the level of the household (all eligible participants in 1 household will receive the same intervention). The randomization plan will be overseen by the Study Statistician. The randomization code and resulting allocation list will be generated and overseen by the Study Statistician. The list will be blocked and stratified by site and risk level.

7.6. Blinding

7.6.1. Patient Blinding

This is a blinded study. However, the medications are not identical-appearing and dosing is different for the active agents so blinding will operate in different ways across those involved in the study, preserving blinding for the participants, those who directly interact with them, and measurement of the study endpoints:

- Participants will be blinded. The bottle of medication they receive will not identify the treatment allocation and only the number and frequency of pills to be taken. If >1 participant per household is randomized, all will receive the same treatment.
- Treating clinicians will be blinded, as the study medication will be dispensed directly to participants.
- Laboratory testing for viral shedding will be blinded, as laboratory staff will not be informed of randomized assignment. It should be noted that the viral shedding endpoint of the trial is an objective assessment, unlikely altered by unmasking, should it occur.
- Study pharmacy staff will be unblinded, as they will prepare the study medication.
- The study statistician will be unblinded for analysis purposes.

Eligible participants will receive one of the following therapies:

- Placebo: Ascorbic acid 1 gm orally twice on Day 1 followed by 500 mg orally twice daily for 9 days (Days 2 to 10)
- LPV/r 800 mg-200 mg orally twice on Day 1, followed by 400 mg-100 mg orally twice daily for an additional 9 days (Days 2 to 10)

HCQ and ascorbic acid will appear similar, and taste will be partially masked as HCQ can be bitter and ascorbic acid will be sour. However, LPV/r will not appear similar to ascorbic acid. Azithromycin and folic acid have the same dosing schedule but are different in shape. Because participants in 1 household will all receive the same assignment and study clinicians will not see the study medication, the blind will be maintained.

The participants will be blinded to their randomization group once assigned. At enrollment, the unblinded Study Pharmacist will use the randomization code revealed at the point of randomization to provide the participant with their group assignment and dispense the allocated study medication in a bottle marked with the study label. The medication and medication information, mid-nasal swabs sufficient to complete the study procedures, *DBS sampling kit, if within the sub-study*, and study instructions will be delivered to the participant.

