1.4. RANDOMIZATION

Due to the adaptive design of the study, we implemented randomization to 12 dummy codes, stratified by site and risk cohort. Participants are randomized to 1 of 12 dummy codes that are mapped to active and control arms using an allocation ratio appropriate to the current design of the study. Participants were randomized 1:1:1 for the Hydroxychloroquine and Hydroxychloroquine + Azithromycin efficacy study.

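### Section 7.6.1 of the protocol tells the unblinded pharmacist to give participants their group assignment, which contradicts the participant blinding stated in the same section

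*Protocol*

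**What the plan says.** The Synopsis describes participants, treating clinicians and the laboratory as blinded, and the pharmacist and statistician as unblinded. Section 7.6.1 of the protocol carries this through:

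- Participants: "The bottle of medication they receive will not identify the treatment allocation and only the number and frequency of pills to be taken".
- Clinicians: "Treating clinicians will be blinded, as the study medication will be dispensed directly to participants".
- Pharmacy: "Study pharmacy staff will be unblinded, as they will prepare the study medication".
- Appearance: "However, LPV/r will not appear similar to ascorbic acid".

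The last paragraph of the section describes enrolment. It opens with "The participants will be blinded to their randomization group once assigned". The following sentence has the unblinded Study Pharmacist "use the randomization code revealed at the point of randomization to provide the participant with their group assignment", and then dispense the drug in a bottle carrying the study label.

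**The concern.** The sentence on blinding and the instruction to the pharmacist concern the same item, the participant's group. One withholds it and the other hands it over. The instruction is operational text, addressed to the person who holds the code at dispensing, so it is the sentence most likely to be turned into a site procedure.

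At stake is the clinical co-primary endpoint. Resolution of COVID-19 symptoms depends largely on what participants enter in the Daily Survey. Participants who know their arm may report symptoms differently, and that difference would be counted as a treatment effect.

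**Working it through.** The documents give no figure on this point, so the check is a comparison of the text.

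**1. Does the bottle itself disclose the arm?** By its wording, no. The label shows only the number and frequency of pills, and Section 7.1 adds an otherwise plain container with a unique identifier. The tablet strengths in Section 7.1 and the regimens in Section 7.6.1 give the same counts in both arms:

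| | LPV/r (200 mg lopinavir per tablet) | Ascorbic acid (250 mg per tablet) |
|---|---|---|
| Each dose, Day 1 | 800 / 200 = 4 tablets | 1000 / 250 = 4 tablets |
| Each dose, Days 2 to 10 | 400 / 200 = 2 tablets | 500 / 250 = 2 tablets |

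Both regimens are taken twice a day, so the printed instructions do not separate the arms.

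**2. Does the pharmacist instruction disclose it?** Read literally, yes. It joins two acts: giving the participant the assignment, and dispensing. The recipient of the first is the participant, and its content is the group to which the preceding sentence says the participant is blinded.

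**3. Does another section correct it?** No. Section 7.5 covers generation of the list, Section 7.8 covers receipt of supplies and adherence, and Section 9.1 covers kits and first doses. None says what the participant is or is not told about the arm. SAP Section 1.4 describes dummy codes but not who may see their mapping.

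**4. Which endpoints are exposed?** Section 4 lists two primary endpoints.

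- *Symptom resolution.* Cough, breathlessness, headache, myalgia, sore throat, chills and loss of smell or taste are reported by the participant (Sections 9.1, 9.2 and 10.1.2). Temperature and SpO2 are self-measured. Hospitalization and death are harder events, but they enter only as failures to resolve. This endpoint is exposed.
- *Viral clearance.* Swabs are self-collected but tested by PCR in a blinded laboratory. Section 7.6.1 itself argues that this endpoint is objective and unlikely to change with unmasking. It makes no such argument for symptoms.

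**5. Does Section 3.2.11 settle the matter?** It accepts that symptom reporting may depend on what participants believe they are taking, and then says the primary endpoints escape this. The sentence names HCQ and ascorbic acid. Section 4 records that the clinical endpoints were initially LRTI, hospitalization and death, and that symptom resolution replaced them in protocol Version 2.0. The reassurance is hard to apply to an endpoint built from reported symptoms.

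**6. How many participants?** The instruction applies to everyone enrolled: 173 per arm x 2 arms = 346 as planned.

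**The case against.** The best defence is that this is a slip of wording. The same sentence goes on to dispensing in a study-labelled bottle, the sentence before it affirms blinding, and the label is designed to conceal the arm. On that reading the pharmacist uses the code to place the participant in a group and select the bottle, and announces nothing. This is probably what was meant, and it stands as an account of intent. It does not remove the contradiction, because the text does not say it and no other section does.

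A second defence is that blinding is already imperfect. The protocol concedes that the products look different, and Section 7.4 has participants counselled extensively about gastrointestinal effects of LPV/r. That also stands, and it limits what the correction can achieve. But a participant who sees only one product need not know which it is, whereas one who is told the group does know.

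**Conclusion.** The point holds as an internal contradiction in Section 7.6.1. If the instruction is followed literally, participant blinding is lost at dispensing for the whole LPV/r comparison, and the self-reported symptom endpoint is open to expectation effects. Viral clearance is little affected. No numerical size can be given: the documents do not say how far knowledge of the arm would shift reported resolution, and any false-positive rate would rest on an invented shift. Nor could such a rate be credited to this phrase alone, since the unmatched products carry their own unblinding risk.

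A reader might go further and infer that recruiting staff could predict the next assignment, because "The list will be blocked and stratified by site and risk level" and informed participants speak with staff on Days 2, 4, 9 and 14 (Section 9.3). The documents do not support this. They give no block size, do not say that blocks are fixed, and do not say that staff learn or track past assignments. Clinicians are stated to be blinded, and only pharmacy staff and the study statistician are described as unblinded.

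A reader might also take SAP Section 1.4, where "Participants are randomized to 1 of 12 dummy codes that are mapped to active and control arms", as proof that codes already shield the arm at this stage. SAP Section 1 limits that document to the first three arms, and its stated ratio is 1:1:1. Use of the codes for LPV/r is not confirmed.

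**What to change.** In Section 7.6.1, delete the words from *provide* up to and including the *and* before *dispense*. The sentence stays grammatical, and the pharmacist then uses the code only to select and dispense the labelled bottle. Add one sentence stating that the code-to-arm mapping is visible only to the pharmacist and the unblinded statistician. Closed reports to the DSMB under Appendix 3 need not change.

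In the same edit, the remark in Section 3.2.11 can be brought into line with the current clinical endpoint. Stating that block sizes are varied and concealed from sites is at most an optional precaution.

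The cost is a few words of protocol text. The change removes a written disclosure step; it leaves the difference in product appearance as it is.

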7.7. Preparation/Handling/Storage/Accountability

Drugs should be stored at room temperature, as per package insert. Records must be maintained that document receipt, release for dosing, disposal, or return to the Sponsor.

7.8. Treatment Compliance

The participant will be contacted to ensure that they received the box of study supplies, were able to collect the first mid-nasal swab and store it appropriately, and took their first day of medication. Participants will be asked to complete a survey that includes information regarding treatment administration. Medication errors, including under-dosing, will be recorded in the survey. *In a sub-study, HCQ, azithromycin, and LPV/r concentrations via a DBS will also be evaluated.*

Consultation via Telehealth, text messaging, or telephone will be available to provide support to the participant to complete study procedures.

7.9. Concomitant Therapy

Participants will be asked about concomitant medications at the screening/baseline evaluation visit. During the study, participants will be asked to complete surveys (Daily Survey and Exit Contact Survey) that include information regarding any medication or vaccine (including over-the-counter or prescription medicines, vitamins, and/or herbal supplements) that the participant receives during the study. At each contact, the Investigator should question the participant about any medication taken.

7.9.1. Prohibited Medications

Medications listed as “Known Risk of Torsades de Pointe” on the website Credible Meds (CredibleMeds.org) will be prohibited with interventions known to prolong the QT interval (including HCQ, azithromycin, and LPV/r). These medications include: quinolone antibiotics (e.g., ciprofloxacin, levofloxacin, and moxifloxacin); macrolide antibiotics (e.g., erythromycin and clarithromycin); methadone; and antiarrhythmic drugs such as Class I (e.g., quinidine, procainamide, and disopromide), Class III (e.g., dofetilide, ibutilide, and sotalol), and amiodarone. Other prohibited medications include cisapride, cilastazol, cimetidine, fluconazole, terfenadine, antipsychotic medications (chlorpromazine, halperidol, and thioridazine), donepezil, oxaliplatin, and the antidepressants citalopram and escitalopram.

Prohibited medications for concomitant administration with HCQ include digoxin, cyclosporin, tamoxifen, anticoagulants (e.g., warfarin), some anticonvulsants, and rifampin. Refer to [Appendix 5](#) for all medications prohibited for coadministration with HCQ.

Prohibited medications for concomitant administration with azithromycin include warfarin. Refer to [Appendix 6](#) for all medications prohibited for coadministration with azithromycin.

Prohibited medications for concomitant administration with LPV/r include drugs that are highly dependent on CYP3A for clearance and for which elevated plasma concentrations are associated with serious and/or life-threatening reactions (e.g., alfuzosin, ranolazine, and simvastatin) and drugs that are potent CYP3A inducers where significantly reduced lopinavir plasma concentrations may be associated with the potential for loss of virologic response (e.g., apalutamide, rifampin, and St. John's Wort). Refer to [Appendix 7](#) for all medications prohibited for coadministration with LPV/r.

7.9.2. *Precautionary Medications*

Use of medications classified as precautionary is not study prohibitory but will be discussed with the study clinician and the participant. These medications include androgens, antidiabetic agents, phenothiazines, artemether, beta-blockers, cardiac glycosides, aminoquinolines, dapsone, herbs, lumefantrine, maitake, mefloquine, monoamine oxidase inhibitors, nelfinavir, pegvisomant, prothionamide, and selective serotonin reuptake inhibitors. Careful monitoring is needed during concomitant use of azithromycin with colchicine or phenytoin. Medications listed as “Possible Risk of Torsades de Pointe” and “Conditional Risk of Torsades de Pointe” on the website Credible Meds (CredibleMeds.org) will be permitted as per discretion of study clinicians and after discussion with the study participant.

7.10. *Treatment After the End of the Study*

No additional treatment will be provided at the end of the study.

8. Discontinuation/Withdrawal Criteria

8.1. *Discontinuation of Study Treatment*

Study treatment will be discontinued for the following reasons:

- Hospitalization
- Requirement for prohibited concomitant medications or other contraindication to study product
- Occurrence of an AE requiring discontinuation of study product, including prolonged QT
- Request by participant to terminate study treatment
- Clinical reasons believed to be life-threatening by the physician, even if not addressed in [Section 7.2](#)

Participants who stop study product should continue study participation off study product with continued evaluations as per the SoA. The reason for study product discontinuation should be recorded.

Hospitalized participants will be followed through hospitalization and the last visit will be within 3 days of discharge.

8.2. *Withdrawal from the Study*

- A participant may withdraw from the study at any time at his/her own request or may be withdrawn at any time for the following reasons:
 - At the request of the primary care provider if he/she thinks the study is no longer in the best interest of the participant
 - Participant is judged by the Investigator to be at significant risk of failing to comply with the provisions of the protocol as to cause harm to self or seriously interfere with the validity of the study results
 - At the discretion of the Institutional Review Board/Ethics Committee or government agencies as part of their duties, Investigator, or industry supporter
- If the participant withdraws consent for disclosure of future information, the Sponsor may retain and continue to use any data collected before such withdrawal of consent.
- If a participant withdraws from the study, he/she may request destruction of any samples taken and not tested, and the Investigator must document this in the site study records.
- See SoA for data to be collected at the time of study discontinuation and follow-up and for any further evaluations that need to be completed.

8.3. *Lost to Follow-up*

A participant will be considered lost to follow-up if he/she is unable to be contacted by the study site.

The following actions must be taken if a participant fails to comply with required study procedures:

- The site must attempt to contact the participant as soon as possible and counsel the participant on the importance of maintaining the assigned procedure schedule and ascertain whether or not the participant wishes to and/or should continue in the study.
- Before a participant is deemed lost to follow-up, the Investigator or designee must make every effort to regain contact with the participant (where possible, 3 telephone calls and, if necessary, a certified letter to the participant's last known mailing address or local equivalent methods). These contact attempts should be documented in the participant's medical record.
- Should the participant continue to be unreachable, he/she will be considered to have withdrawn from the study with a primary reason of lost to follow-up.

9. Study Encounters

The current COVID-19 pandemic has placed a significant burden on the healthcare system. For this study, specimen and data collection will be conducted to minimize impact of non-ill participants within the healthcare system. If the participant is assessed as eligible, contact between study participants and study personnel will occur via a Health Insurance Portability and Accountability Act (HIPAA)-compliant video conference (Telehealth). Optionally, contact with the study clinician or staff after Day 1 may be conducted by telephone.

Participants will be instructed to seek clinical care should they manifest any signs or symptoms of LRTI requiring medical intervention and notify their physician about trial participation.

9.1. *Screening/Baseline Evaluation: Day 0/1*

Participants will be assessed for study eligibility through a screening conducted through a web-based screening tool, HIPAA-compliant video conference (Telehealth), telephone, or text messaging.

Day 0 evaluations are as follows:

- Informed consent
- Collection of demographic information
- Sign HIPAA form
- Collection of past and current medical conditions, including known pregnancy and/or lactation status
- Collection of concomitant medication information
- Collection of information (including laboratory documentation of COVID-19 testing)
- Check of inclusion and exclusion criteria

Eligible participants will be randomized. Participants will receive a monitoring kit via courier, which will include thermometer and SpO₂ device. They will be instructed on how to self-assess respiratory rate. In addition, they will receive a swab kit via courier or mail, which includes a study instruction booklet, swabs, plastic tubes for swab collection, a return box with affixed Category B UN3373 label, as required by International Air Transport Association (IATA) guidelines ([UN3373 Medical Packaging 2020](#)), and a pre-paid return shipping label.

The participant will do the following on Day 1:

- Collect mid-nasal swab for PCR
- Complete Daily Survey (online, telephone, or text messaging). This survey will include confirmation of adherence to study therapy dosing and daily swab collection, concomitant medication review, AEs, and symptoms review and objective measures including SpO₂, respiratory rate, temperature, pulse, and ECG*. In addition, the modified inFLUenza patient-reported outcome (Flu-PRO) survey will be completed.
- Take study therapy (LPV/r or placebo [ascorbic acid]), as assigned
- *May collect DBS sample for analysis of HCQ, azithromycin, and LPV/r concentrations.*

Instructions for skin puncture and DBS sample preparation are provided in [Appendix 9](#). A study team member will be available via Telehealth, telephone, or text messaging to provide support for completion of this study procedure.

Screening (Day 0) and Day 1 procedures can occur on the same day.

The SARS-CoV-2 positive test results will be confirmed through laboratory records or through detailed description of testing as described by participant.

9.2. Day 2 Through Day 13

The participant will do the following every day from Day 2 through Day 13, inclusive:

- Collect mid-nasal swab for PCR
- Take study therapy until Day 10 (inclusive) for LPV/r, or ascorbic acid (as assigned)
- Complete Daily Survey (online, telephone, or text messaging). This Survey will include confirmation of adherence to study therapy dosing and daily swab collection, concomitant medication review, AEs, and symptoms review and objective measures including SpO₂, respiratory rate, temperature, pulse, and ECG. ECG measurements may be recorded on Days 2 through 11 only*. In addition, the modified Flu-PRO survey will be completed.
- *If in DBS sub-study, collect DBS samples for analysis of HCQ, azithromycin, or LPV/r concentrations at any time during this period (1 to 5 times) after study drug dosing has commenced.*
- **EKG monitoring may not be necessary if HCQ/AZ are not used.*

A study team member will be available via Telehealth, text messaging, or telephone to provide support for completion of study procedures. The courier will collect the swabs at minimum within 1 or 2 days of Day 7 and Day 13 and potentially as frequently as daily.

9.3. Days 2 (± 1 day), and Days 4, 9, and 14 (± 2 days)

Contact with study clinician or staff will be conducted via telemedicine (Telehealth) or telephone. Participants will be clinically assessed for signs and symptoms of respiratory distress and will have in person assessment of AEs. As needed, additional contact with the study clinician or staff will be conducted at the request of the participant (e.g., if developing concerning symptoms or an adverse event) or if needed to clarify study procedures or follow-up symptoms.

9.4. Days 14 and 21

The participant will do the following on Days 14 and 21:

- Collect mid-nasal swab for PCR
- Complete Daily Survey (online, telephone, or text messaging). This survey will include confirmation of adherence to study therapy dosing and daily swab collection, concomitant medication review, AEs, and symptoms review and objective measures including SpO₂, temperature, and pulse. In addition, the modified Flu-PRO and WHO Ordinal Scale for Clinical Improvement surveys will be completed.

The courier will collect the swabs of Day 14 and Day 21 with the Day 28 swabs.

9.5. Day 28

The participant will do the following on Day 28:

- Collect mid-nasal swab for PCR
- Complete the Exit Contact Survey (online, telephone, or text messaging). This survey will include confirmation of adherence to study therapy dosing and daily swab collection, concomitant medication review, AEs, and symptoms review and objective measures including SpO₂, temperature, and pulse. In addition, the modified Flu-PRO and WHO Ordinal Scale for Clinical Improvement surveys will be completed.
- *If in DBS sub-study, collect DBS sample for analysis of HCQ, azithromycin, or LPV/r concentrations as well as detection of anti-SARS-CoV-2 antibodies.*

For participants who are hospitalized on Day 28, the Day 28 procedures will be performed within 3 days after discharge from the hospital.

A study team member will be available via Telehealth, text messaging, or telephone to provide support for completion of study procedures.

The courier will collect the swabs at minimum within 1 or 2 days of Day 28.

Clinical outcomes will be confirmed through the electronic health record, if possible.

Participant Reimbursement

Participants will be reimbursed on Day 28 or at the post discharge visit. No reimbursement will be provided for unscheduled Telehealth visits requested by the participants for support with study procedures.

10. Study Assessments and Procedures

- Study procedures and their timing are summarized in the SoA.
- Protocol waivers or exemptions are not allowed.
- Immediate safety concerns should be discussed with the Sponsor immediately upon occurrence or awareness to determine if the participant should continue or discontinue study treatment.
- Adherence to the study design requirements, including those specified in the SoA, is essential and required for study conduct.
- All baseline evaluations must be completed and reviewed to confirm that potential participants meet all eligibility criteria. The Investigator will maintain a screening log to record details of all participants screened and to confirm eligibility or record reasons for screening failure, as applicable.
- Procedures conducted as part of the participant's routine clinical management and obtained before signing of the informed consent form may be utilized for screening or baseline purposes provided that the procedures met the protocol-specified criteria and were performed within the time frame defined in the SoA.
- *Blood samples will only be collected as a part of a sub-study. The maximum amount of blood collected from each participant over the duration of the study, including any extra assessments that may be required, will not exceed 10 mL.*

